# 6 Overview of Planned Analyses

# 6.1 Analyses for the Safety Monitoring Committee Meetings

For Parts A and C, the Safety Monitoring Committee (SMC) will regularly meet to evaluate safety and tolerability data (adverse events [AEs], safety laboratory data, electrocardiogram [ECG], and vital signs), PK data, and PD (parasitemia) data (Part C only). Details of the SMC meetings and related analysis methodology are covered in the SMC Charter.

# 6.2 Final Analysis

All final, planned analyses identified in the Clinical Study Protocol and in this IAP will be performed only after the last subject has completed the double-blind (as applicable) treatment phase of the study with all study data in-house, all data queries resolved, and the database locked. Details of the final PK, PD, and safety/tolerability analyses are further described in the PK (Section 16.1), PD (Section 16.2), and safety/tolerability sections (Section 15), respectively.

A data review meeting will be held prior to database lock. In addition, no database can be locked and no randomization code should be unblinded until this IAP has been approved for the final analyses.

# 7 Changes to the Planned Analyses in the Clinical Study Protocol

In the clinical trial protocol, the PK parameters, area under the curve from time zero (dosing time) to 24 hours postdose (AUC0-24h) and dose-normalized AUC0-24h (AUC0-24h/Dose), were specified for calculation for single doses (ie, Part A, and Part C if applicable) for the purpose of

combining/comparing PK exposures between single doses and multiple doses (ie, Part B). Since Part B is not being conducted, these parameters are not being calculated for Parts A and C.

A correlation analysis of M5717 concentrations from dried blood spot (DBS) assay and whole blood will be performed as described in Section 16.1.3.

# 8 Protocol Deviations and Analysis Sets

## 8.1 Definition of Protocol Deviations and Analysis Sets

Important protocol deviations or events are protocol deviations and events that might significantly affect the completeness, accuracy, and/or reliability of the study data or that might significantly affect a subject's rights, safety, or well-being.

A subset of these important protocol deviations or events that lead to the exclusion of a subject from an analysis set (see Section 8.2) are considered clinically important.

The following important deviations or events will be identified and confirmed prior to or at the Data Review Meeting:

- Subjects who are dosed on the study despite not satisfying the inclusion criteria
- Subjects who develop withdrawal criteria whilst on the study but are not withdrawn
- Subjects who receive the wrong treatment or an incorrect dose
- Subjects who receive an excluded concomitant medication
- Deviation from Good Clinical Practice (GCP)
- Other events/factors related to PK and/or PD, which include, but may not be limited to, events
  that could affect PK and/or PD, will be evaluated on a case-by-case basis:
  - Vomiting following oral dosing (these instances will be discussed on a case-by case basis)
  - Sample processing errors that may lead to inaccurate bioanalytical or PD results
  - Incomplete data (due to lost samples, insufficient sample volumes for assay, etc.)
  - Inaccurate dosing or dosing errors
  - Inadequate fasting prior to and following dosing
  - Concomitant medication violations (refer to Section 6.5.2 of Clinical Study Protocol), that could affect PK or PD.

In case of a deviation or event that may affect PK and/or PD data, collected PK and/or PD data which is likely to be affected may be excluded from the study results after consultation and agreement with Sponsor or sponsor representative. These deviations or events could be classified as clinically important and confirmed prior to or at the Data Review Meeting before database lock and unblinding of Part A. Other changes to the procedures or events which do not significantly impact the quality of the PK and/or PD data will not lead to exclusion from the PK and/or PD Analysis Sets. A common example of an event which usually does not lead to exclusion from the

PK Analysis Set is a missed PK blood sample or deviations from PK blood collection times, with the requirement that the actual time of collection is recorded.

In the case subjects or data are excluded from the PK and/or PD Analysis Sets, their PK and/or PD data will be listed in the CSR and flagged.

All protocol deviations will be documented in Study Data Tabulation Model (SDTM) datasets whether identified through site monitoring, medical review, or programming.

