3.1 Malaria

According to the latest estimates, released in December 2016 by World Health Organization, worldwide there were about 212 million cases of malaria in 2015 (with an uncertainty range of 148 million to 304 million) and an estimated 429,000 deaths (with an uncertainty range of 235,000 to 639,000) (1). Most deaths (70%) occur among children below the age of 5 years, mainly in Africa. Human malaria is caused by 4 Plasmodium parasite species (*P. falciparum*, *P. vivax*, *P. malariae* and *P. ovale*), transmitted to humans by Anopheles mosquitoes, called “malaria vectors”. *P. falciparum* and *P. vivax* are the most common. *P. falciparum* is the deadliest whereas *P. vivax* triggers a recurrent form of malaria that, if left untreated, may lead to severe illness.

Malaria is an acute febrile illness. In a nonimmune individual, symptoms appear from 7 days up to 15 days after the infective mosquito bite. The first symptoms – fever, headache, chills and vomiting – may be mild and difficult to recognize as malaria. If not treated within 24 hours, *P. falciparum* malaria can progress from acute clinical disease to severe illness often leading to death. Children with severe malaria frequently develop one or more of the following symptoms: severe anemia, respiratory distress in relation to metabolic acidosis, or cerebral malaria. Also in adults, multiple organs are usually involved. In malaria-endemic areas, persons may develop partial immunity, resulting in > 80% of infections being asymptomatic in regions of high transmission. Non severe malaria of all 4 Plasmodium parasite species can be cured with proper treatment.

The goal of drug combination therapy for parasitic diseases such as malaria is to prevent the emergence of resistance, while providing additional benefit for the treatment by providing a higher cure rate. The rationale behind the development of artemisinin-based combination therapies was to combine a very fast-acting compound (an artemisinin derivative) that will destroy > 80% of the parasites within the first 24 hours (reducing symptoms rapidly) with a long-acting compound, such

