5.2.8 Safety Monitoring Committee and Decision Criteria

The SMC will be set up as described in the SMC charter.

The SMC will determine:

- Dose escalation/de-escalation
- Termination of further dose escalation in Part A if it is expected that further escalation will not be tolerated or if it is determined that a maximum exposure may be reached (Section 5.5.3)
- The need to start a multiple dosing regimen in Part B
- The timing to start Part C
- The respective dose(s) and dose escalations to be evaluated in Part B and Part C
- Request unblinding of data, if deemed necessary
- Suspension of enrollment, trial modification, or trial termination.

Part A and Part B

The SMC will regularly meet at approximately Day 25 after all subjects in a given SAD/MAD cohort have received administration of M5717 or matching placebo. A medical monitoring report summarizing all safety and tolerability data (AEs, safety laboratory data, ECG, and vital signs) collected from minimally 6 subjects up to and including Day 11 (around 1 median half-life) for SAD cohorts will be provided to the SMC for review. The medical monitoring report may also include a summary of the safety data for all previous dose cohorts, when appropriate. The first 2 SMC meetings in the SAD part (Part A) will also contain PK data from 6 subjects up to 144 hours postdose. For later SMC meetings, PK data of the preceding cohort(s) will be reviewed as applicable to support the safety and tolerability assessment, as deemed necessary by the SMC. Safety laboratory and PK data included in the monitoring report to be provided to the SMC will undergo quality control by the respective laboratory(ies) responsible for this data.

In addition, the SMC can modify PK sampling times and/or ECG recording times based on new information received (eg, to better align with timing of t_{max}) but is not allowed to increase the number of PK sampling points unless by amending the clinical trial protocol.

CCI

In case of a safety concern, the SMC members are allowed to request immediate unblinding of the data. In the pivotal toxicology studies, vomiting and diarrhea were identified as dose-limiting events, so these events will be carefully monitored. The SMC may also request access to unblinded PK data in case the need arises, to evaluate the correlation between exposure and safety data reviewed by the SMC.

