# 8.2 Definition of Analysis Sets and Subgroups

For purposes of analysis, the following populations are defined:

|                       | ,  |  |  |
|-----------------------|--|--|--|
| Population            | Description  |  |  |
| Enrolled              | The Enrolled Analysis Set will include all subjects who provided signed informed consent, regardless of treatment status in the study. This set will be used for subject disposition.  |  |  |
| Safety (SAF)          | The Safety Analysis Set will include all subjects who receive investigational medicinal product (M5717 or placebo for Part A; M5717 for Part C). Subjects will be analyzed according to the actual treatment they receive.   |  |  |
| Pharmacokinetics (PK) | The Pharmacokinetic Analysis Set will consist of all subjects who receive M5717, have no clinically important protocol deviations or important events affecting PK, and provide at least one (measurable) postdose concentration. Subjects will be analyzed according to the actual treatment they receive. All PK analyses will be based on this analysis set. Subjects who receive placebo will not be part of the Pharmacokinetic Analysis Set. |  |  |
| Pharmacodynamics (PD) | The Pharmacodynamic Analysis Set will be defined for Part C only. The Pharmacodynamic Analysis Set will include all subjects who receive M5717 in Part C without clinically important protocol deviations or important events affecting PD. Subjects in the Pharmacodynamic Analysis Set must have evaluable postdose PD data. All PD analyses will be based on this analysis set.   |  |  |

With respect to the use of the analysis sets in the different analyses, it could be presented in a table such as the following:

| Analyses                       | Enrolled
Analysis Set | Safety
Analysis Set | PK Analysis
Set | PD Analysis
Set |
|--------------------------------|--------------------------|------------------------|--------------------|--------------------|
| Subject Disposition            | ✓                        |                        |                    |                    |
| Baseline Assessments           |                          | ✓                      |                    |                    |
| Past and Concomitant Therapies |                          | ✓                      |                    |                    |
| Compliance and Exposure        |                          | ✓                      |                    |                    |

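### Part C exclusions from the PD analyses are case by case and not outcome-blind, and no planned summary shows PRR or recrudescence with the excluded subjects included

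*SAP*

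**What the plan says.** SAP 8.1 lists events that can affect PK or PD and are judged one by one. The list is open: "Other events/factors related to PK and/or PD, which include, but may not be limited to, events" that could affect either. One entry reads "Vomiting following oral dosing", to be discussed individually, with no time window or other objective rule. Data likely to be affected "may be excluded from the study results after consultation and agreement with Sponsor or sponsor representative". Such events could be classed as clinically important and "confirmed prior to or at the Data Review Meeting before database lock and unblinding of Part A". SAP 8.1 defines clinically important deviations or events as those important ones that lead to exclusion from an analysis set.

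SAP 8.2 restricts the PD Analysis Set to Part C subjects who received M5717 "without clinically important protocol deviations or important events affecting PD" and who have evaluable post-dose PD data. It bases all PD analyses on that set. Protocol 8.5.2.3 likewise estimates PRR, the primary PD variable, on the PD Analysis Set.

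Several safeguards are stated. Excluded PK or PD data are listed and flagged (SAP 8.1), reasons for exclusion are listed (SAP 10.2.2), and excluded parasitemia data are listed and flagged (SAP 16.2.2). SAP 10.2.1 adds a rule for PK concentrations only: erroneous values may be dropped if this is agreed before any statistical analysis, and values that merely look implausible must stay in.

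**The concern.** The timing rule in SAP 8.1 protects a blinded part of the trial. Part C has no blind to protect, and the people who agree an exclusion can already know the subject's parasite curve. A discretionary exclusion made with the outcome in view can shift the estimate in either direction, even when everyone acts in good faith.

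Vomiting is the ground that matters most. Protocol 3.1 names it among the first symptoms of malaria ("headache, chills and vomiting"), and Protocol 5.2.8 records that in the pivotal toxicology studies "vomiting and diarrhea were identified as dose-limiting events". Protocol 7.4.4.7 keeps a subject who vomits in the trial without re-dosing, so that subject's concentrations and parasitemia can still be measured. Low measured exposure with a measured parasite response is useful information for the primary PK-to-PRR objective. Losing part of a dose is a good reason to leave the subject out of a dose-based PK summary. It is not a reason to leave the subject out of an analysis that uses measured concentrations.

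At stake are the cohort PRR, the recrudescence count and the exposure-response relationship, each resting on 8 subjects per dose.

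**Working it through.** **Who knows what, and when**

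- Part C is open-label (Protocol 5.2.4 and 6.10).
- qPCR takes about 4 hours and is read in real time to guide rescue (Protocol 5.2.4).
- The Safety Monitoring Committee reviews PK/PD data to at least Day 9 after each Part C cohort (Protocol 5.2.8). Its members include the sponsor's clinical pharmacology representative and statistician (Protocol 2).
- Exclusions need sponsor agreement and are settled at or before the Data Review Meeting (SAP 8.1). By then each cohort's parasitemia has been seen by sponsor functions.

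**Inputs**

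- Cohort size is 8 (Protocol 8.1). The planned totals reproduce: 3 × 8 = 24 for Part C, and 88 + 24 + 24 = 136 overall.
- The documents give no between-subject SD for log10 PRR. I assume 0.3–0.5, with 0.2–0.6 as a wider range.
- No power or alpha figure applies, because the trial is descriptive (Protocol 8.5.1).

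**Worst-case shift in PRR.** Take 8 normally distributed subject-level log10 PRR values with equal weights. The expected extreme of 8 standard normals is 1.424 SD from the mean, and the next is 0.852 SD.

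- Slowest one excluded: shift = 1.424 / 7 = 0.203 SD.
- Slowest two excluded: shift = (1.424 + 0.852) / 6 = 0.379 SD.

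On the PRR scale the factor is 10^(shift × SD). For one exclusion:

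- SD 0.3: 10^(0.203 × 0.3) = 1.15.
- SD 0.5: 10^(0.203 × 0.5) = 1.26.
- Wider range: 1.10 at SD 0.2 and 1.33 at SD 0.6.

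A simulation of 400,000 cohorts of 8 gives the same shifts (0.204 and 0.380 SD). Coverage of a nominal 95% t-interval for the cohort mean is:

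| Excluded | Coverage |
|---|---|
| none | 95.0% |
| slowest 1 of 8 | 89.7% |
| slowest 2 of 8 | 80.5% |

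**Recrudescence.** Exact 95% intervals before and after one recrudescent subject is excluded:

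| All 8 | After one exclusion |
|---|---|
| 4/8 = 50.0% (15.7–84.3) | 3/7 = 42.9% (9.9–81.6) |
| 2/8 = 25.0% (3.2–65.1) | 1/7 = 14.3% (0.4–57.9) |
| 1/8 = 12.5% (0.3–52.7) | 0/7 = 0% (0–41.0) |

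These shifts are small against the intervals. The last row matters most, because the observed result changes from some recrudescence to none.

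**Limits of the arithmetic.** It ranks subjects by outcome and removes the slowest, so it is an upper illustration and not a forecast. Protocol 8.5.2.3 weights subject slopes by inverse variance, so 0.203 SD need not carry over exactly.

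**The case against.** The strongest reply is that the discretion is bounded and visible. SAP 8.1 requires a deviation or event and data likely to be affected. It says that events without a significant effect on data quality do not lead to exclusion, and it settles decisions before database lock. With 8 subjects per cohort and the listings described above, a reader could identify any excluded subject and see that subject's data. All of this stands. A reader might infer that exclusions are unlimited or hidden, and the documents do not support that. The listings do not, however, give the estimate with the subject included, and deciding before lock is not the same as deciding without knowledge of the outcome.

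A second reply is that vomiting need not remove anyone from PRR, since the PD set drops only events affecting PD. That is a permissible reading, but SAP 8.1 treats vomiting as an event that could affect PK and/or PD and does not settle which. It is also tempting to say that vomiting after dosing tracks parasite burden, or that it is dose-limiting in people. Protocol 3.1 describes malaria in general, the dose-limiting statement concerns toxicology studies, and the SAP's trigger can be read simply as a concern about lost dose. Neither claim is shown for Part C.

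Third, removing recrudescent subjects would work against the plan's own aim. Protocol 5.2.4 needs enough recrudescence to derive the minimal inhibitory concentration, and Protocol 8.1 seeks data on both cure and recrudescence. This stands, and it is why no direction of bias can be asserted.

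Finally, SAP 16.2.1 and 16.2.3 place the PD parameter methods and the PK/PD modelling in separate documents, which may hold stricter rules. That is possible, but this SAP defines the PD set, binds all PD analyses to it, and points to no such rule.

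**Conclusion.** The point holds as a gap in the analysis plan. Part C PD exclusions are discretionary, need sponsor agreement and are not outcome-blind. The rule that keeps implausible values in covers PK concentrations only, and no planned summary re-estimates PRR or recrudescence with excluded subjects restored.

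The worst case for one exclusion per cohort of 8 is a rise of about 0.20 between-subject SD in mean log10 PRR. That is 15–26% on the PRR scale, and it rests on normality, equal weights, an assumed SD of 0.3–0.5 log10, and the excluded subject being the slowest clearer. A reader might conclude that the primary result will be favourably biased. The documents do not support that: an exclusion needs a triggering event, nothing shows that the affected subject would be the slowest, and the direction in practice is unknown. This is an inexpensive improvement worth making in a descriptive trial with small cohorts.

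**What to change.** Amend the SAP for Part C in three places.

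1. Present PRR and recrudescence for all dosed Part C subjects with valid post-dose qPCR data, beside the PD Analysis Set results. Remove only documented sample or assay errors, and analyse subjects by the dose actually received.
2. State that vomiting after dosing may remove a subject from dose-based PK summaries, but not from PRR, recrudescence or exposure-response analyses that use measured concentrations.
3. Extend the SAP 10.2.1 rule to parasitemia: values are excluded only for documented errors agreed before statistical analysis, and never because they look implausible.

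Listings without results at the Data Review Meeting would not be a substitute, since investigators and sponsor members of the committee will already have seen the parasite curves. Showing both sets of results does not depend on anyone being blind.

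The cost is SAP wording, one extra set of tables, and slightly more spread in the all-dosed summaries. Trial conduct does not change.

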# 8.2 Definition of Analysis Sets and Subgroups

For purposes of analysis, the following populations are defined:

|                       | ,  |  |  |
|-----------------------|--|--|--|
| Population            | Description  |  |  |
| Enrolled              | The Enrolled Analysis Set will include all subjects who provided signed informed consent, regardless of treatment status in the study. This set will be used for subject disposition.  |  |  |
| Safety (SAF)          | The Safety Analysis Set will include all subjects who receive investigational medicinal product (M5717 or placebo for Part A; M5717 for Part C). Subjects will be analyzed according to the actual treatment they receive.   |  |  |
| Pharmacokinetics (PK) | The Pharmacokinetic Analysis Set will consist of all subjects who receive M5717, have no clinically important protocol deviations or important events affecting PK, and provide at least one (measurable) postdose concentration. Subjects will be analyzed according to the actual treatment they receive. All PK analyses will be based on this analysis set. Subjects who receive placebo will not be part of the Pharmacokinetic Analysis Set. |  |  |
| Pharmacodynamics (PD) | The Pharmacodynamic Analysis Set will be defined for Part C only. The Pharmacodynamic Analysis Set will include all subjects who receive M5717 in Part C without clinically important protocol deviations or important events affecting PD. Subjects in the Pharmacodynamic Analysis Set must have evaluable postdose PD data. All PD analyses will be based on this analysis set.   |  |  |

With respect to the use of the analysis sets in the different analyses, it could be presented in a table such as the following:

| Analyses                       | Enrolled
Analysis Set | Safety
Analysis Set | PK Analysis
Set | PD Analysis
Set |
|--------------------------------|--------------------------|------------------------|--------------------|--------------------|
| Subject Disposition            | ✓                        |                        |                    |                    |
| Baseline Assessments           |                          | ✓                      |                    |                    |
| Past and Concomitant Therapies |                          | ✓                      |                    |                    |
| Compliance and Exposure        |                          | ✓                      |                    |                    |
| PK Analysis                    |                          |                        | ✓                  |                    |
| PD Analysis                    |                          |                        |                    | ✓                  |
| Safety and Tolerability        |                          | ✓                      |                    |                    |

No subgroup analyses are planned.

# 9 General Specifications for Data Analyses

Data will generally be presented separately for each part (Part A or Part C) of the study, although some combination of data across parts may be done, where appropriate (see Section 16.1.3).

Details on PK and PD data presentation can be found in Section 16.

# Listings

All listings will be sorted by treatment/dose, subject, and/or nominal time point, as appropriate. Data which are only measured before administration of the investigational medicinal product (IMP) will be sorted by subject and nominal time point (if appropriate).

Safety data will be reported and analyzed with the same precision as the source data provided, regardless of how many significant figures or decimal places the data carry.

